5.5.2 Dose Modifications for Atezolizumab

There will be no dose modifications for atezolizumab.

Table 3: Recommended guidelines for management of general adverse events Atezolizumab Dose Modifications.

Grade (CTCAE)	Recommended dose modification
Grade 1 or 2	No action required

Grade 3 and 4	
• Interrupt dosing of atezolizumab.• If AE resolves to Grade \leq 1, then restart dosing of atezolizumab at fixed dose level.• If the AE does not resolve to Grade \leq 1 permanently discontinue atezolizumab.• If the Grade 3/4 AE recurs (a second time), atezolizumab should be discontinued.
---------------	--

Additional guidelines for specific adverse events are provided in the subsections below and the specific management guidelines are highlighted in Appendix 7 for cobimetinib plus atezolizumab.

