5.5.1 Dose Modifications for Cobimetinib

NOTE: Investigators can interrupt dosing of atezolizumab (or cobimetinib) depending on the attribution of the toxicity, which is at the discretion of the investigator. During this time, treatment may continue with the other non-attributable treatment agent.

NOTE: If either atezolizumab or cobimetinib are discontinued, dosing with the other drug may continue at the discretion of the investigator.

NOTE: For Grade ≥ 3 toxicities associated primarily with laboratory abnormalities only, study treatment may continue without interruption and/or dose reduction at the discretion of the investigator per institutional practice.

Table 2: Recommended Cobimetinib Dose Modifications

Grade (CTCAE)	Recommended dose modification
Grade 1 or Grade 2 (tolerable)	No dose reduction. Maintain cobimetinib at the same dose of 60 mg QD (3 tablets)
Grade 2 (intolerable) or Grade 3 or 4 (any)*	
First appearance	Interrupt treatment until Grade ≤ 1 , restart treatment at 40 mg QD (2 tablets)
Second appearance	Interrupt treatment until Grade ≤ 1 , restart treatment at 20 mg QD (1 tablet)
Third appearance	Consider permanent discontinuation

* If cobimetinib is withheld for > 28 days because of toxicity, the patient should be discontinued from cobimetinib, unless resumption of treatment is approved by the Medical Monitor after discussion with the investigator.

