5.5.4 Specific Dose Modifications for cobimetinib

Withhold cobimetinib for NCI CTCAE intolerable Grade ≥ 2 toxicity.

When restarting therapy after withholding treatment for a toxicity that has resolved to baseline or grade ≤ 1 :

- Reduce cobimetinib dose to 40 mg
- Reduce cobimetinib to 20 mg for second appearance of intolerable Grade ≥ 2 toxicity.
- Permanently discontinue cobimetinib on third appearance of intolerable Grade ≥ 2 toxicity unless the benefits for the individual patient are deemed to outweigh the risks.

For detailed recommendations regarding management of certain AEs, i.e. gastrointestinal toxicity (diarrhea), hepatotoxicity, rash, pulmonary toxicity, eye toxicity and cardiotoxicity, see Appendix 7.

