6.1.2.7 Severe Hepatotoxicity (Grade ≥3)

Liver laboratory test abnormalities, including increases in ALT, AST, and alkaline phosphatase, have been reported as adverse events and serious adverse events in patients treated with cobimetinib and vemurafenib. Generally, elevations in liver laboratory tests have been managed effectively with dose modifications.

Guidelines for management of patients who develop elevations in ALT, AST, and/or bilirubin are provided in Appendix 6.

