Appendix 7 Anaphylaxis Precautions

PRECAUTIONS

Equipment needed:

- Tourniquet
- Oxygen
- Epinephrine for subcutaneous, intravenous (IV), and/or endotracheal use in accordance with standard practice
- Antihistamines
- Corticosteroids
- IV infusion solutions, tubing, catheters, tape

PROCEDURES

In the event of a suspected anaphylactic reaction during study drug infusion, the following procedures should be performed:

[figure not shown]
1. Stop the drug infusion.
2. Apply a tourniquet proximal to the injection site to slow systemic absorption of study drug. Do not obstruct arterial flow in the limb.
3. Maintain adequate airway.
4. Administer antihistamines, epinephrine, or other medications as required by patient status and directed by physician in charge.
5. Continue to observe the patient and document observations.

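### Ten of eleven pointers to the toxicity-management rules cite the wrong appendix, and the general dosing rules in Section 5.5 conflict with the rules those pointers should reach

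*Combined protocol and SAP*

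**What the plan says.** The contents list and the appendix headings agree: Appendix 6 holds the guidelines for managing adverse events of the combination, Appendix 7 is headed "Appendix 7 Anaphylaxis Precautions", and Appendix 8 is the biomarker analysis.

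The body text mostly points elsewhere. Section 5.5.2 states that "the specific management guidelines are highlighted in Appendix 7 for cobimetinib plus atezolizumab". Section 5.5.4 lists the toxicities that need detailed recommendations and ends "eye toxicity and cardiotoxicity, see Appendix 7". Only Section 6.1.2.7, on hepatotoxicity, is right: guidance on ALT, AST "and/or bilirubin are provided in Appendix 6".

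Section 5.5 also has dosing rules of its own:

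- **Cobimetinib, Table 2 of Section 5.5.1.** For Grade 1 or tolerable Grade 2: "Maintain cobimetinib at the same dose of 60 mg QD (3 tablets". For the first intolerable Grade 2 event, or the first Grade 3 or 4 event of any kind, interrupt until Grade 1 or better, then "restart treatment at 40 mg QD (2 tablets". A toxicity hold of more than 28 days ends cobimetinib unless the Medical Monitor approves resumption.
- **Cobimetinib, Section 5.5.4.** On restarting after resolution: "Reduce cobimetinib dose to 40 mg". Permanent discontinuation comes only at the third appearance, with an exception for individual benefit.
- **Atezolizumab, Table 3 of Section 5.5.2.** No action for Grade 1 or 2. For Grade 3 or 4, interrupt, and if the event resolves to Grade 1 or better, "then restart dosing of atezolizumab at fixed dose level".

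**The concern.** An investigator who meets a serious toxicity will look in Section 5.5. If the general rules there matched Appendix 6, a wrong appendix number would be a copy-editing matter. They do not match. For several named events Appendix 6 stops a drug for good, while Section 5.5 restarts or continues it. The sentences that should carry the reader from the general rule to the specific one name an appendix that contains no dose rules. At stake is whether a patient could be restarted on, or kept on, a drug that the protocol's own event-specific rule stops.

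**Working it through.** No formula or sample-size figure is involved. The check is a count of pointers and a row-by-row comparison.

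**1. Pointers to the toxicity-management rules (correct target: Appendix 6).**

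| Cited | Sections | Count |
|---|---|---|
| Appendix 7 (wrong) | 5.3.1, 5.3.2, 5.5.2, 5.5.3, 5.5.4, 6.1.2.1, 6.1.2.2, 6.1.2.4, 6.1.2.5, 6.1.2.6 | 10 |
| Appendix 6 (right) | 6.1.2.7 | 1 |

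So 10 of 10 + 1 = 11 are wrong. Inside Section 5.5 (5.5.2, 5.5.3, 5.5.4) it is 3 of 3.

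**2. Pointers to the anaphylaxis precautions (correct target: Appendix 7).** Sections 5.3.1 and 5.5.3 and the opening table of Appendix 6 all cite Appendix 8: 3 of 3 wrong.

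**3. Other wrong appendix numbers, unrelated to toxicity.** Sections 4.3.2 and 5.6.5 cite Appendix 5 for immune-modified RECIST (it is 4). Section 5.6.6 twice cites Appendix 9 for biomarkers (it is 8, and there is no Appendix 9). Section 4.1 cites Appendix 6 for RECIST v1.1 (it is 2). That is 2 + 2 + 1 = 5. The overall total is 10 + 3 + 5 = 18, of which 10 + 3 + 2 + 2 = 17 are exactly one too high. This pattern fits an appendix having been removed without the text being renumbered.

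**4. Cobimetinib: Appendix 6 against Table 2 and Section 5.5.4, first occurrence.**

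| Event permanently stopping cobimetinib | Place in Appendix 6 | Drugs stopped | Section 5.5, once resolved |
|---|---|---|---|
| Severe hypersensitivity | Opening table | Both | Restart at 40 mg |
| Grade 4 diarrhea | Table A3-1 | Both | Restart at 40 mg |
| Grade 4 colitis | Table A3-1 | Both | Restart at 40 mg |
| AST/ALT > 10 × ULN | Table A3-2 | Both | Restart at 40 mg, or continue under the third NOTE in 5.5.1 |
| Grade 4 dermatologic event | Table A3-3 | Both | Restart at 40 mg |
| Grade 3/4 pneumonitis | Table A3-4 | Both | Restart at 40 mg |
| Retinal vein occlusion, any grade | Ocular toxicity table | Cobimetinib | Keep 60 mg if Grade 1 or tolerable Grade 2; otherwise restart at 40 mg |
| Grade 4 or any-grade cerebral hemorrhage attributed to cobimetinib | Hemorrhage rows | Cobimetinib | As for retinal vein occlusion |

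That is 6 + 2 = 8 events. Life-threatening hepatic events, stopped for both drugs in the combined AST/ALT and bilirubin row of Table A3-2, make 9. The comparison takes severe hypersensitivity and AST/ALT > 10 × ULN as at least Grade 3. The hypersensitivity line gives no grade; Table A3-2 labels the band just below 10 × ULN as Grade 3. The third NOTE in Section 5.5.1 lets treatment continue for Grade 3 or higher toxicities that are mainly laboratory abnormalities. It sits outside Table 2, so correcting the table alone would not reach it.

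**5. Atezolizumab: Appendix 6 against Table 3.** Section 5.5.3 already stops atezolizumab for life-threatening immune-mediated events. Footnote c of Appendix 6 allows rechallenge with documented approval from the investigator and the Medical Monitor. The remaining conflicts are mainly:

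- Grade 3 pneumonitis;
- severe hypersensitivity that is not life-threatening;
- Grade 4 events not judged immune-mediated;
- Grade 2 colitis and Grade 2 pneumonitis, where Appendix 6 withholds both drugs and Table 3 takes no action.

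**The case against.** The strongest reply is that the protocol already sets a general-then-specific order. Table 3 is titled for general adverse events, Sections 5.5.2 and 5.5.4 send the reader on to event-specific guidance, and both tables are headed as recommendations. The last row of Appendix 6, for toxicities not described elsewhere in it, gives largely the same actions as Tables 2 and 3. On that reading the tables are only the default for unlisted events.

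Much of this stands as evidence of intent. It does not settle the text. No sentence gives Appendix 6 priority, Table 2 is not labelled general and covers Grade 3 or 4 events of any kind, and the sentences that imply the order name the wrong appendix.

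Other limits also stand. Section 5.5 preserves the investigator's judgment. Sections 5.3.1, 5.3.2 and 5.5.3 also refer to the Investigator's Brochures, which cannot be seen here. The general rules restart only after resolution, and Table 2 requires Medical Monitor approval after a hold of more than 28 days.

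Two stronger readings are tempting and not supported. A reader might infer that both drugs are equally affected; Section 5.5.3 and footnote c make the atezolizumab conflict clearly narrower, and footnote c offers nothing comparable for cobimetinib. A reader might also infer that patients were wrongly re-exposed or that the efficacy result is affected; nothing in the documents shows either.

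**Conclusion.** The point holds as a minor safety-conduct defect. Ten of eleven pointers to the toxicity rules are wrong, as are all three anaphylaxis pointers. Table 2 and Section 5.5.4 would restart cobimetinib, or Table 2 would maintain it, after at least eight listed events (nine with life-threatening hepatic events) for which Appendix 6 permanently stops it. The atezolizumab conflict is confined to the situations in step 5 of the working.

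The conclusion assumes that Section 5.5 is read as written, without an unstated rule that Appendix 6 prevails. A careful reader can recover from the contents list. How many patients would be affected is unknown and could be zero. No effect on ORR is claimed.

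**What to change.** (a) Correct the appendix numbers: 7 to 6 in Sections 5.3.1, 5.3.2, 5.5.2, 5.5.3, 5.5.4, 6.1.2.1, 6.1.2.2, 6.1.2.4, 6.1.2.5 and 6.1.2.6; 8 to 7 in Sections 5.3.1 and 5.5.3 and in the opening table of Appendix 6. As housekeeping with no bearing on toxicity management, change 5 to 4 in Sections 4.3.2 and 5.6.5, 9 to 8 (twice) in Section 5.6.6, and 6 to 2 in Section 4.1.

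(b) Add at the start of Section 5.5:

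> For any event listed in Appendix 6, the Appendix 6 action (withhold, permanently discontinue, or resume) applies instead of Tables 2 and 3, Section 5.5.4 and the NOTES in Section 5.5.1; Tables 2 and 3 apply to events not listed there. After a permanent discontinuation, atezolizumab rechallenge is possible only where the row carries footnote c, with the approval it requires.

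Both parts are needed: correcting the numbers alone would leave two contradictory instructions. The insertion must cover withholding as well as permanent stops, or the Grade 2 colitis and pneumonitis conflicts remain. The severe hypersensitivity line carries no footnote c, so rechallenge would not be open there.

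The cost is 18 number corrections and one short insertion, with no new data or procedures. Investigators lose a little flexibility for listed events. Where Appendix 6 resumes cobimetinib without stating a dose reduction, as for Grade 2 pneumonitis, the sponsor should say whether Table 2's reduction still applies.

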5.5.3 Specific Dose Modifications for atezolizumab

Toxicities associated or possibly associated with atezolizumab treatment should be managed according to standard medical practice. Additional tests, such as autoimmune serology or biopsies, may be used to determine a possible immunogenic etiology. Although most immune-mediated adverse events observed with immunomodulatory agents have been mild and self-limiting, such events should be recognized early and treated promptly to avoid potential major complications. Discontinuation of atezolizumab may not have immediate therapeutic effect, and in severe cases, immune-mediated toxicities may be acutely managed with topical corticosteroids, systemic corticosteroids, or other immunosuppressive agents.

The primary approach to Grade 1 and 2 immune-mediated adverse events is supportive and symptomatic care with continued treatment with atezolizumab; for higher grade immune-mediated adverse events, atezolizumab should be withheld and oral/parenteral steroids administered. Recurrent Grade 2 immune-mediated adverse events may also mandate withholding atezolizumab or the use of steroids. Consideration for benefit-risk balance should be made by the investigator, with consideration of the totality of information as it pertains to the nature of the toxicity and the degree of clinical benefit a given patient may be experiencing prior to further administration of atezolizumab.

Atezolizumab should be permanently discontinued in patients with life-threatening immune-mediated adverse events. Patients who discontinue atezolizumab treatment may still remain in the study until loss of clinical benefit. Management of systemic immune activation is presented below.

See the atezolizumab Investigator's Brochure and Appendix 7 for details on management of gastrointestinal, dermatologic, endocrine, pulmonary toxicity, hepatotoxicity, potential pancreatic or eye toxicity and other immune-mediated adverse events. See Appendix 8 for precautions for anaphylaxis.

Systemic Immune Activation

Systemic immune activation is a rare condition characterized by an excessive immune response. Given the mechanism of action of atezolizumab, systemic immune activation is considered a potential risk when given in combination with other immunomodulating agents. Systemic immune activation should be included in the differential diagnosis for patients who, in the absence of an alternative etiology, develop a sepsis-like syndrome after administration of atezolizumab, and the initial evaluation should include the following:

- CBC with peripheral smear
- PT, PTT, fibrinogen, and D-dimer
- Ferritin

- Triglycerides
- AST, ALT, and total bilirubin
- LDH
- Complete neurologic and abdominal examination (assess for hepatosplenomegaly)

If systemic immune activation is still suspected after the initial evaluation, contact the PI for additional recommendations.

5.5.4 Specific Dose Modifications for cobimetinib

Withhold cobimetinib for NCI CTCAE intolerable Grade ≥ 2 toxicity.

When restarting therapy after withholding treatment for a toxicity that has resolved to baseline or grade ≤ 1 :

- Reduce cobimetinib dose to 40 mg
- Reduce cobimetinib to 20 mg for second appearance of intolerable Grade ≥ 2 toxicity.
- Permanently discontinue cobimetinib on third appearance of intolerable Grade ≥ 2 toxicity unless the benefits for the individual patient are deemed to outweigh the risks.

For detailed recommendations regarding management of certain AEs, i.e. gastrointestinal toxicity (diarrhea), hepatotoxicity, rash, pulmonary toxicity, eye toxicity and cardiotoxicity, see Appendix 7.

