Asymptomatic CPK elevation, Grade 4	
 Withhold cobimetinib and atezolizumab treatment. If improved to Grade \leq 3 within 4 weeks, restart cobimetinib at a dose reduced by 20 mg, if clinically indicated. If not, permanently discontinue cobimetinib. Resumption of atezolizumab may be considered in patients who are deriving benefit.
Rhabdomyolysis or symptomatic CPK elevations	
 Withhold cobimetinib and atezolizumab treatment. If event improves by at least one grade and symptoms resolve within 4 weeks, restart cobimetinib at a dose reduced by 20 mg, if clinically indicated. If not, permanently discontinue cobimetinib. Resumption of atezolizumab may be considered in patients who are deriving benefit after discussion with the Medical Monitor.
Hemorrhage	
Grade 3 hemorrhage other than cerebral hemorrhage	
 Withhold cobimetinib. Continue atezolizumab. Clinical judgment should be applied when considering whether cobimetinib should be resumed. There are no data on the effectiveness of cobimetinib dose modification for hemorrhage events. If cobimetinib cannot be resumed within 28 days, permanently discontinue cobimetinib.
Grade 4 hemorrhage or any grade cerebral hemorrhage	
 Permanently discontinue cobimetinib if the event is attributed to cobimetinib; otherwise, withhold cobimetinib. Continue atezolizumab. Clinical judgment should be applied when considering whether cobimetinib should be resumed. There are no data on the effectiveness of cobimetinib dose modification for hemorrhage events.

CPK = creatine phosphokinase.

Event	Action to Be Taken
Grade 3 or 4 or intolerable	
 Withhold atezolizumab and cobimetinib.
Grade 2 treatment-related toxicities not described above	
 If event resolves to Grade 1 or better within 12 weeks, resume atezolizumab at fixed dose. If not, permanently discontinue atezolizumab. ^{a,b,c} If event resolves to Grade 1 or better within 28 days, resume cobimetinib with dose reduced by one level. If not, permanently discontinue cobimetinib.

^a If corticosteroids have been initiated, they must be tapered over \geq 1 month to \leq 10 mg/day oral prednisone or equivalent before atezolizumab can be resumed.

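### The general triggers for withholding cobimetinib do not match: Table 2 in section 5.5.1 acts on Grade 3 or 4 toxicity regardless of tolerability, while section 5.5.4 requires intolerability at every grade from 2 up

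*Combined protocol and SAP*

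**What the plan says.** Three places set a general rule for interrupting cobimetinib.

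- **Section 5.5.1, Table 2.** The action row is headed "Grade 2 (intolerable) or Grade 3 or 4 (any", with the last word in brackets. At first appearance, treatment stops until Grade 1 or lower, then "restart treatment at 40 mg QD (2 tablets"; the second appearance leads to 20 mg, and at the third, permanent discontinuation is to be considered. A NOTE above the table covers Grade 3 or higher toxicities that are primarily laboratory abnormalities; for these, "study treatment may continue without interruption and/or dose reduction at the discretion of the investigator per institutional practice".
- **Section 5.5.4.** The opening instruction is "Withhold cobimetinib for NCI CTCAE intolerable Grade" 2 or higher. The step to 20 mg depends on a second appearance that is again intolerable, and the last step reads "Permanently discontinue cobimetinib on third appearance of intolerable Grade" 2 or higher, unless benefit is judged to outweigh risk.
- **Appendix 6, residual row.** It applies to "Grade 3 or 4 or intolerable" "Grade 2 treatment-related toxicities not described above", and the first action is "Withhold atezolizumab and cobimetinib".

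Appendix 6 also has event-specific rows. Those for diarrhea, dermatologic events and serous retinopathy act on cobimetinib at Grade 3 with no tolerability condition. Section 5.5 introduces all of this as guidance that does not displace the investigator's clinical judgment.

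**The concern.** Table 2 and section 5.5.4 set a general rule for the same decision on the same drug, but tolerability has a different role in each. In Table 2 it divides Grade 2 events and is irrelevant above that. In 5.5.4 it is required at all grades from 2 up. The condition recurs at the second and third appearances in 5.5.4, so it is hard to treat as a single misplaced word.

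At stake are consistent safety handling, cobimetinib dose intensity, and what counts as a protocol deviation. Both sections step the dose down by counting appearances, so an event that counts in one and not in the other shifts every later step.

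**Working it through.** The plan states no figure on this point, so the check is a comparison of the rules case by case.

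| Event | 5.5.1 Table 2 and NOTE | Appendix 6 | 5.5.4 trigger | Result |
|---|---|---|---|---|
| Intolerable Grade 2, treatment-related, no row of its own | Interrupt | Withhold both drugs | Met | Agree |
| Tolerable Grade 3, non-laboratory, treatment-related, no row of its own (e.g. fatigue) | Interrupt | Withhold both drugs (residual row) | Not met | Mismatch |
| Tolerable Grade 3 diarrhea or rash | Interrupt | Withhold both drugs (own row) | Not met | Mismatch |
| Tolerable Grade 3 serous retinopathy | Interrupt | Interrupt cobimetinib (own row) | Not met | Mismatch |
| Asymptomatic Grade 3 CPK elevation | May continue (NOTE) | Continue both drugs | Not met | No necessary conflict |
| AST/ALT in the row labelled Grade 3, bilirubin below 2 × ULN | May continue (NOTE) | Continue study treatment; withhold atezolizumab if immune-related is suspected | Not met | No necessary conflict on cobimetinib |

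**Effect on dose steps.** Take a patient on 60 mg with treatment-related fatigue, first at Grade 3 and tolerable, later at Grade 2 and intolerable.

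- Table 2: the first episode is the first appearance (restart at 40 mg), and the second episode is the second appearance (restart at 20 mg).
- 5.5.4: the first episode does not meet the trigger, so the second is the first appearance that counts (restart at 40 mg).
- Difference after the same history: 40 − 20 = 20 mg, one dose level.

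**Scale.** Section 2.7 reports rates at Grade 3 or higher in 90 patients on the combination: diarrhea 7.8%, fatigue 7.8%, rash 4.4%. Assume that these rates carry over to 60 patients:

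- diarrhea: 60 × 0.078 = 4.7
- fatigue: 60 × 0.078 = 4.7
- rash: 60 × 0.044 = 2.6

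The tolerable share is not given. Under that assumption, the expected number with a mismatched event lies between 0 and 4.7 for diarrhea, 0 and 4.7 for fatigue, and 0 and 2.6 for rash. Patients may overlap, so these should not be added.

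**Does another provision settle it?** No precedence rule was found. Section 5.5.2 says that further guidance on specific events follows in the subsections below, and 5.5.4 is titled as specific modifications, so a reader could take it to override Table 2. For certain events 5.5.4 sends the reader to Appendix 7 for detail, but that appendix covers anaphylaxis; adverse event management is in Appendix 6.

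**The case against.** The strongest reply is that 5.5.4 is only loosely drafted. It never tells anyone to continue cobimetinib through a tolerable Grade 3 event; it is silent where Table 2 is explicit. Elsewhere the tolerable/intolerable split is used only at Grade 2, and no place names a tolerable Grade 3 or 4 category. The severity scale in section 6.4.2.5, for events not listed in CTCAE, describes Grade 3 as severe or medically significant and Grade 4 as life-threatening, so few such events may be tolerable once laboratory findings are set aside. For diarrhea, rash and eye toxicity, 5.5.4 itself defers to an appendix for detail. Table 2 is labelled as recommended, investigator judgment is preserved, and section 5.6 requires assessment before each dose.

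Much of this stands. It narrows the affected class and makes a drafting slip plausible. It does not remove the mismatch: nothing says that Grade 3 or higher is by definition intolerable, Table 2 keeps the two ideas apart, the deferral points to the wrong appendix, and preserving judgment does not say which default it starts from.

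A reader might infer more than the documents support:

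- *That Appendix 6 interrupts for any Grade 3 or 4 toxicity.* It does not. Two rows continue cobimetinib at Grade 3, and the residual row covers only treatment-related events without their own row.
- *That the sections order opposite actions.* One trigger is met and the other is not; 5.5.4 contains no instruction to continue.
- *That the toxicity stopping rule is distorted.* Section 5.10.5 counts a qualifying event when it occurs, whether or not drug is then withheld.
- *That about 28 of 60 patients are affected*, from the 46.1% with Grade 3 events in section 2.5.2.1 (60 × 0.461 = 27.7). That rate comes from a single-agent study with several doses and schedules and includes laboratory events. It is a loose ceiling on Grade 3 events, not a count of tolerable non-laboratory ones.

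**Conclusion.** The inconsistency is real but narrow. It concerns tolerable, non-laboratory Grade 3 or 4 toxicity: Table 2 calls for interruption, as does Appendix 6 at Grade 3 through its residual row (if treatment-related) or the rows named above, while the 5.5.4 trigger is not met. The consequence that can be shown is a shift of one dose level for the same history. The number of patients cannot be derived from the documents. The conclusion rests on reading intolerable in 5.5.4 as qualifying every grade from 2 up, which is what the sentence says and what its later steps repeat. It should be corrected because it bears on patient handling and on how dose steps are counted. The fault is internal wording, not the design, and no view is taken on which trigger is right.

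**What to change.** Reconcile section 5.5.4, Table 2 in section 5.5.1 and the residual row of Appendix 6 so that one trigger applies to tolerable Grade 3 and 4 events. Use the same wording to define what counts as a first, second or third appearance. State how the laboratory NOTE and the event-specific rows of Appendix 6 relate to that general trigger. Correct the pointer in 5.5.4 from Appendix 7 to Appendix 6. The sponsor and investigators choose the rule.

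The cost is a wording amendment in a few places. It needs no new data, procedures or patients, and no change to the statistical analysis.
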